Mystical Experience and Anxiety: Finally, we wish to examine the association between undergoing a peak or mystical experience during psilocybin-assisted psychotherapy and subsequent reduction in anxiety. Presence and features of mystical experiences will be measured via a self-report instrument administered 24 hours after each experimental session, and self-boundary changes will be assessed via a self-report instrument administered at baseline, 24 hours after each experimental session and two weeks after the second experimental session. When applicable, occurrence of mystical experiences and changes in self-boundary will be assessed 24 hours after each open-label session.

General Investigational Plan

Drug Description and Doses

Participants will either receive 4 or 25 mg psilocybin (4-phosphoryloxy- N,N-dimethyl-tryptamine) in opaque capsules on two separate psilocybin-assisted psychotherapy sessions to occur seven to 14 days apart.

The full experimental intervention dose of psilocybin was chosen on the basis of early psilocybin psychotherapy research (Passie 2005) and recent studies of psilocybin's ability to produce mystical or spiritual experiences in healthy individuals with prior spiritual practice (Griffiths et al. 2006; Hasler et al. 2004). The dose is slightly lower on average than Griffiths and colleagues' dose of 30 mg/70 kg and is expected to produce all the cardinal effects of serotonergic hallucinogens, including changes in visual perception, rapid and sometimes profound changes in mood, derealization and depersonalization (feeling as if the world or the self are not real, feeling "as if in a dream") and unusual experiences relating to the body and the self. These effects are expected to facilitate therapeutic effects, including generation of a peak or mystical experience, reassessment of world view, perception of the body or the self, and re-appraisal or feelings of mastery over anxiety. This dose is also expected to overcome any potential blunting of effects arising from concurrent use of opiates in pain management medication (Grob 2007).

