The active placebo in this study will be a low dose of the investigational drug. Active placebo dose of psilocybin was chosen on the basis of early and recent studies of psilocybin in humans (Hasler et al. 2004; Isbell 1959; Moreno et al. 2006; Passie et al. 2002). This dose was chosen for its ability to produce a few of the effects of psilocybin without producing any of the potentially therapeutic effects. People may perceive lights or colors as being brighter and sounds as being different, and they may experience slight changes in mood, cognition or perception. A 4 mg dose of psilocybin is not expected to generate a mystical or transformative experience.

Sample Population and Subjects

The study will enroll nine (9) individuals with the following criteria listed below. Study drop-outs or withdrawals will be replaced until nine participants have completed the randomized phase of the study. Study completion will be defined as attending visits from screening up through the follow-up two weeks after the second psilocybin-assisted session. Participants who are unable to complete or withdraw from the open-label phase or before the two-month follow-up phase will not be replaced. Inclusion Criteria

Inclusion Criteria

Prospective participants must meet the following inclusion criteria listed below to be eligible for study enrollment.

1. Have been diagnosed with Stage IV melanoma with a life expectancy of one year or less
2. Meet diagnostic criteria for anxiety on the SCID, or a score of 8 or higher on the HADS Anxiety score.
3. Diagnosis must be a new diagnosis of anxiety subsequent to diagnosis with melanoma.
4. Are 18 years or older,
5. Live with another adult who is their primary caregiver, who can also provide transportation to and from the cancer center for each experimental session and who also consents to take part in a parallel investigation of anxiety and depression in primary caregivers. The same caregiver may remain overnight with participants after each psilocybin session.
6. Have a Mini-Mental State Exam score of 27 or higher.
7. Are willing to commit to medication dosing, experimental sessions with overnight stay, traveling to follow-up sessions, and to complete the evaluation instruments.
8. Are willing to refrain from taking any anti-depressants during the study period.
9. Are willing to refrain from taking any benzodiazepines during the 24 hours preceding each scheduled psilocybin, placebo, or open label session.

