The sponsor or the investigator (following consultation with the sponsor) has the right to discontinue this study at any time. If the trial is prematurely terminated, the investigator is to promptly inform the study subjects and she or he should assure appropriate therapy and follow-up. If the trial or study is prematurely discontinued, all procedures and requirements pertaining to the archiving of the documents will be observed. All other study materials will be returned to the sponsor, will be treated in accordance with federal and local regulations. DEA requires destruction of unused schedule 1 drugs in studies.

Data Analysis

The primary analyses for this study will be a repeated measures analysis of variance (ANOVA) with condition (active placebo versus experimental dose) as a between-subject

factor and time of administration (baseline versus two weeks after the second experimental psilocybin-assisted session) as a repeated measure. The investigators will employ separate repeated measures ANOVAs to examine the effects of psilocybin-assisted psychotherapy on all outcome variables, including the primary outcome variable. Separate analyses will be performed for HADS, HAM-A and STAI anxiety scores, HADS and HAM-D depression scores, EORTC-QLQ-C15 scores, FACIT-Sp scores and NK cell counts. The investigators will perform post-hoc tests (as Tukey's test) on any statistically significant interactions. Probability of rejecting the null hypothesis will be set at 0.05. Because of the pilot nature of this study and small sample size, we will not employ Bonferroni corrections for when examining analyses results for measures of anxiety. In the case of pain levels measured by daily diary, the investigators will perform two repeated measures ANOVAs comparing average pain levels at baseline versus average pain levels for the weeks immediately after the first and after the second experimental sessions, with p. set at 0.05. The investigators are interested in discovering whether there are differences in pain level between active placebo and experimental dose participants immediately after undergoing psilocybin-assisted psychotherapy.

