If at least four participants complete measures during the follow-up two months after the second experimental or open-label psilocybin-assisted therapy session, then the investigators will perform separate repeated-measures ANOVAs on the anxiety, depression, quality of life and spirituality scores listed above, with p. set at 0.05. The investigators are chiefly interested in differences between baseline and two-month follow-up scores. If a sufficient number of participants complete pain measures on the date of the two-month follow-up session, then the investigators will perform a t-test to compare VAS pain ratings on the day of the two-month follow-up with the average pre-psilocybin pain rating.

Given that only three participants will be eligible for the open-label phase of the study, the investigators do not plan to perform formal comparisons between anxiety, depression, spirituality or quality of life across the randomized and open-label study phases. However, the investigators will perform informal observations and present descriptive statistics for all outcome variables two weeks after the second open-label psilocybin-assisted session.

Before analyzing differences between degree of mystical experiences or changes in spiritual identity for active placebo and experimental dose participants, the investigators will first perform a matched-sample t test to determine whether there were significant differences between mystical experience (SCQ) and self-concept boundary/spiritual identity (SELF) scores measured after each of the two psilocybin-assisted sessions. If there are no significant differences between SCQ and SELF scores after the first and the second psilocybin session, then the investigators will compute the average between the two scores and employ the average SCQ and SELF score in nearly all subsequent analyses of these scores. Subsequent analyses will include an analysis of variance comparing SCQ and SELF scores in active placebo and full-dose participants, and correlational analyses of anxiety (HADS and STAI) and depression (HADS) scores as related to SCQ and SELF scores, with p. set at 0.05. The investigators may also compare

SCQ scores and NK cell counts made from blood sampled approximately 23 hours after each psilocybin-assisted session to see whether there are associations between presence and degree of mystical experience changes in immunological function.

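### A nine-person matched t-test decides whether SCQ and SELF scores are averaged over the two sessions, and no analysis is named if it is significant

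*Protocol*

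**What the plan says.** Under Data Analysis, before any dose-group comparison of mystical experience or spiritual identity, "the investigators will first perform a matched-sample t test to determine whether there were significant differences" between the SCQ and SELF scores taken after each of the two psilocybin sessions. The rule that follows is "If there are no significant differences between SCQ and SELF scores after the first and the second psilocybin session, then the investigators will compute the" mean of the two. That mean then serves widely, since the plan is to "employ the average SCQ and SELF score in nearly all subsequent analyses of these scores". The later analyses named are an analysis of variance between the dose groups and correlations with HADS and STAI anxiety and HADS depression.

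The section gives no equivalence margin, agreement measure or power for this pretest, and does not say what is analysed when it is significant. The general significance statement in the same section is "Probability of rejecting the null hypothesis will be set at 0.05". The number of pairs follows from Sample Population and Subjects: "Study drop-outs or withdrawals will be replaced until nine participants have completed the randomized phase of the study". The Randomization section puts six of the nine on 25 mg and three on 4 mg.

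The scores serve the last of the Secondary Objectives: "Finally, we wish to examine the association between undergoing a peak or mystical experience during psilocybin-assisted psychotherapy and subsequent reduction in anxiety".

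**The concern.** The pretest is asked a question it cannot answer. It examines whether the mean change from session 1 to session 2 is zero, at a sample size where all but very large changes go unseen, and its result then picks the variable for almost every later SCQ and SELF analysis. Failing to reject at nine pairs does not show that the sessions gave similar scores. Nor does the test look at agreement within a person: if some participants have their strongest experience in session 1 and others in session 2, the mean change can be near zero while individual pairs differ widely.

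At stake is the choice of outcome variable for the mystical-experience objective. The two-session mean is the more precise summary, and it is kept or dropped on a result that may be chance, with nothing stated to take its place.

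**Working it through.** **Inputs.** Nine completers (Sample Population and Subjects); six on 25 mg, three on 4 mg (Randomization); level 0.05 (Data Analysis), taken as two-sided. The between-session correlation r is not in the protocol and is varied as an assumption.

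**The plan's own figure first.** Statistical Power gives 0.1143 for a two-sample t-test, 6 versus 3, effect size 0.6. Noncentral t with 7 df and noncentrality 0.6 × √(6×3/9) = 0.849 gives 0.1143 two-sided (0.190 one-sided). The figure reproduces and supports the two-sided reading. The protocol states no power for the pretest.

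**Power of the pretest.** Paired t-test, n = 9, 8 df, noncentrality dz × √9, where dz is the mean shift divided by the SD of the paired differences.
- dz = 0.5: noncentrality 1.5, power 0.263, so the shift is missed 73.7% of the time.
- 80% power needs dz of about 1.07. At dz = 0.5 it needs 34 pairs.
- The 95% interval for the mean shift has half-width 2.306/√9 = 0.77 SD of the differences.

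**In between-person SD units.** For a shift of 0.5 between-person SD, dz = 0.5/√(2(1−r)):

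| r | dz | probability of averaging |
|---|---|---|
| 0 | 0.354 | 0.845 |
| 0.25 | 0.408 | 0.809 |
| 0.5 | 0.500 | 0.737 |
| 0.7 | 0.645 | 0.600 |

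So for a fixed non-zero shift, poorer agreement makes averaging more likely. With no mean shift the test passes 95% of the time at every r, so it never detects poor agreement. If the same shift occurs only in the six 25 mg participants, simulation of the pooled test gives averaging in 91%, 87% and 76% of trials at r = 0, 0.5 and 0.8.

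**What averaging does to the dose comparison.** Simulating 6 versus 3 with no dose effect, the dose-group t-test on the two-session mean, among trials with a non-significant pretest, rejects in about 5% at session shifts of 0, 0.5 and 1 SD.

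**What losing the mean costs.** For a dose difference of 1.5 between-person SD:
- one session: noncentrality 1.5 × √2 = 2.121, power 0.45;
- two-session mean at r = 0.5: its SD is √((1+0.5)/2) = 0.866, the standardised difference is 1.5/0.866 = 1.732, noncentrality 2.449, power 0.56.

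**If either session's test could be claimed after a significant pretest** (no dose effect, r from 0 to 0.7, shift in between-person SD):
- within that branch, false positives are about 8% to 10%;
- overall, about 5% with no session shift, about 6% at 0.5 SD, and about 7% to 8% at 1 SD.

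**The case against.** The strongest reply is that the miss rate describes the harmless outcome. When the pretest fails to see a shift, the plan uses the two-session mean, which is the summary recommended here, and the dose comparison keeps its 5% error rate. A 25 mg-only shift, or peaks split between sessions, also ends in averaging. That stands: a reader might infer that the 74% miss rate corrupts the dose comparison, and it does not.

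Second, a reader might infer that the plan declares the two sessions equivalent or interchangeable. The text says neither; it only says the scores will be averaged and used in nearly all later analyses.

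Third, a reader might infer that the plan builds in two chances of a positive dose comparison. The protocol is silent on what follows a significant pretest. A repeated measures ANOVA with session as a factor would fit that silence equally well and would carry no inflation, and a statistical analysis plan not at hand may settle it. The error rates and the power loss above are therefore conditional, not features of the stated plan.

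Fourth, this is an openly low-powered pilot, and SCQ and SELF are listed as process measures. That limits the importance of the point but does not rescue the rule, because a small sample is exactly where a non-significant result says least.

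**Conclusion.** The point holds as a fault in a stated method, confined to a secondary objective. The protocol itself fixes a data-driven gate: the two-session mean is used only if a matched t-test on about nine pooled participants is non-significant. That test has power 0.26 for a shift of half an SD of the paired differences and is blind to within-person disagreement when the mean shift is zero, so its result is no basis for choosing the variable.

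The practical harm lies in the significant branch, where the more precise summary is abandoned with nothing named instead. Its size rests on assumptions: a power loss from 0.56 to 0.45 if single-session tests follow (r = 0.5, 1.5-SD dose difference), and overall false positives of about 6% to 8% if either session may be claimed and the sessions truly differ by 0.5 to 1 between-person SD. With no session shift the overall rate is about 5%. The HADS anxiety primary analysis is unaffected.

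**What to change.** - Delete the matched t-test as a condition for averaging.
- Compare the dose groups with the repeated measures ANOVA the plan already uses elsewhere: condition between subjects, session (1, 2) within subjects. Its condition effect is the contrast of the two-session means and is valid whether or not the sessions differ.
- Name the two-session mean in advance as the SCQ and SELF summary for the correlations, whatever the session difference turns out to be.
- Report the session difference as an estimate with its 95% interval rather than as a pass or fail.
- Optionally, repeat the correlations with the higher of the two session scores, since the objective concerns having had a peak experience.

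The cost is rewording one paragraph. No data, visits or participants are added.

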All outcome measures selected for this study were chosen because they are well-recognized in the literature and because they are or will be used in related pilot studies, allowing comparison across these investigations. The primary outcome measure for this study will be the HADS anxiety score. The investigators will also measure anxiety with the STAI and the HAM-A. The investigators will assess depression with HADS depression scores and with the HAM-D. Participant beliefs about life purpose and spirituality will be measured with the FACIT-Sp, spirituality in relation to self-concept by the SELF, and quality of life will be assessed with the EORTC-QLQ-C15. Daily pain levels will be assessed via participant response on a visual analog scale, and daily pain and anxiety medication use will serve as an indirect measure of anxiety and experienced pain. Natural killer cell counts will serve as a measure of innate immune system function.

All participants will be screened via SCID and HADS, as described above in “Screening”. The investigators will also use MMSE scores to assess study eligibility and mental competence throughout the course of the study.

The SCQ will serve as a process measure, assessing presence and degree of effects of psilocybin, and the SELF will serve as a process measure of self-boundary change. The KRPS, a measure frequently employed in studies of people with cancer, will serve as a means of rating performance status.

Table 1: List of assessments for use in this study. Time listed in minutes.

Assessment	Abbreviation	Measure of	Time needed	Clinician rated	Participant Self-rated	Purpose of Assessment/Measure
Daily Medication Diary	--	Anxiolytic & pain management meds	5 min		X	Outcome
Daily Pain Level Diary	--	Daily pain levels	5 min.		X	Outcome
Europ. Organiz. For Research and Treatment of Cancer; Quality of Life Questionnaire-C15	EORTC QLQ-C15	Global quality of life	5-10 minutes.		X	Outcome
Functional Assessment of Chronic Illness Therapy-spirituality	FACIT-Sp	Spiritual or life purpose beliefs	5 min.		X	Outcome
Hamilton Anxiety Rating Scale	HAM-A	Anxiety	5-10 min	X		Outcome
Hamilton Depression Rating Scale	HAM-D	Depression	5-10 min	X		Outcome
Hospital Anxiety and Depression Scale#	HADS	Anxiety + Depression	5-10 min.		X	Screening & Outcome
Karnofsky Performance R__ Scale	KPRS	Everyday life function	5 minutes	X		Supplemental
Mini Mental State Examination	MMSE	Mental status / competency	15 minutes	X		Screening, continued eligibility

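### The named SELF analyses use post-session scores with no baseline term, although the stated question is change and a Visit 3 SELF is scheduled

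*Protocol*

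**What the plan says.** Three places in the protocol set the SELF question as change. Secondary Objectives (Mystical Experience and Anxiety) states that "self-boundary changes will be assessed via a self-report instrument administered at baseline"; the later SELF time points are the day following each session and the two-week visit. Assessments and Measures states that "the SELF will serve as a process measure of self-boundary change". The SELF paragraph of Data Analysis opens by announcing an analysis of "changes in spiritual identity for active placebo and experimental dose participants".

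That paragraph then names these steps. The scores after the first and second sessions are compared by a matched-sample t test. If they do not differ, the rule is to "compute the average between the two scores and employ the average SCQ and SELF score in nearly all subsequent analyses of these scores". The arm comparison is "an analysis of variance comparing SCQ and SELF scores in active placebo and full-dose participants". The association analysis is "correlational analyses of anxiety (HADS and STAI) and depression (HADS) scores as related to SCQ and SELF scores, with p. set at 0.05". Baseline SELF is not mentioned in any step.

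The baseline is meant to exist. Time and Events marks SELF at Visits 3, 6, 9 and 10, and the baseline form in Appendix B has fields for its subscales and total. The separate baseline-versus-two-week ANOVAs name the anxiety and depression scales and "EORTC-QLQ-C15 scores, FACIT-Sp scores and NK cell counts", but not SELF.

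**The concern.** The SCQ rates the session itself, so it has no baseline and a post-session score is the right variable. SELF is handled in the same sentence and the same way, but it measures a standing characteristic that participants bring with them and it has a pre-treatment value.

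Two things follow if the paragraph is carried out as named. The arm comparison contrasts levels, so any chance difference in starting self-expansiveness between six and three participants passes partly into it. The correlation with anxiety mixes two sources: people who were already more self-expansive, and people whose self-boundary shifted in the session. Only the second bears on the objective. The protocol's own background (Disease History and Related Research) reports that existential well-being goes with lower anxiety, so a link between a standing trait and anxiety is plausible on the protocol's own premises.

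**Working it through.** **Inputs.** Allocation six versus three (Randomization); alpha 0.05 (Data Analysis); effect size 0.6 and stated power 0.1143 (Statistical Power). The correlation r between Visit 3 SELF and the post-session SELF entered in the analysis is not in the protocol. It is assumed here over a range, with equal SDs at the two times.

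**1. The plan's own figure.** No power is stated for SELF, but the two-sample calculation has the same layout. Noncentrality = 0.6 × √(6×3/9) = 0.849 on 7 df. The exact two-sided t-test power is 0.1143, as stated.

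**2. Chance imbalance at baseline.** SE = √(1/6 + 1/3) = 0.707 SD. The difference exceeds 0.5 SD in 48% of randomisations and 1 SD in 16%. These percentages say how often an imbalance occurs. They are not error on top of the post-only test, whose variance already contains it.

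**3. What passes into the arm contrast.** A post-only difference is shifted by r × imbalance. For an imbalance of one SE at r = 0.7, that is 0.7 × 0.707 ≈ 0.5 SD.

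**4. Precision and power.** The 95% half-width relative to post-only is √(2(1−r)) for a change score. For ANCOVA it is √(1−r²) × √(1+1/5) × t(6)/t(7). The last columns give power at a true effect of 0.6 SD, from 200,000 simulated trials of six versus three.

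| r (assumed) | Width, change | Width, ANCOVA | Power, post-only | Power, change | Power, ANCOVA |
|---|---|---|---|---|---|
| 0.3 | 1.18 | 1.08 | 0.11 | 0.09 | 0.11 |
| 0.5 | 1.00 | 0.98 | 0.11 | 0.11 | 0.12 |
| 0.7 | 0.78 | 0.81 | 0.11 | 0.16 | 0.16 |
| 0.8 | 0.63 | 0.68 | 0.11 | 0.21 | 0.20 |

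Overall type I error was 0.05 for all three methods.

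**5. When the imbalance has happened.** Among simulated trials with no drug effect in which the full-dose arm started more than 0.71 SD higher:

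| r (assumed) | Mean difference: post-only | Change | ANCOVA | Rejection: post-only | Change | ANCOVA |
|---|---|---|---|---|---|---|
| 0.5 | 0.54 | −0.54 | about 0 | 0.09 | 0.08 | 0.05 |
| 0.7 | 0.76 | −0.32 | about 0 | 0.11 | 0.07 | 0.05 |
| 0.9 | 0.97 | −0.11 | about 0 | 0.14 | 0.06 | 0.05 |

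A change score over-corrects for the imbalance. With two time points, the condition-by-time interaction in a repeated-measures ANOVA is the test of the change score, so it shares this behaviour.

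**6. The correlation.** Suppose Visit 3 SELF correlates c with the anxiety variable (size assumed 0.3 to 0.5) and session-induced change has no link to anxiety once Visit 3 is given. Then:

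- Raw post-session SELF still correlates r × c with anxiety. This runs from 0.5 × 0.3 = 0.15 to 0.9 × 0.5 = 0.45 for r from 0.5 to 0.9.
- A simple SELF change score correlates (r×c − c)/√(2−2r). This has the opposite sign, with size about 0.07 to 0.25 over the same grid.
- The partial correlation given Visit 3 SELF is 0.

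**The case against.** The strongest reply is that randomisation already protects the arm comparison. That stands. A reader might infer from the baseline omission that the full-dose result is systematically biased, or that the 48% and 16% figures are added error. Neither is supported: the post-only test is unbiased on average, holds its 5% level and carries the imbalance in its standard error. The raised rejection rates in step 5 arise only after conditioning on an unlucky draw, under an assumed r.

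A second reply is that the text leaves room. The later analyses are introduced as an open list, the average is to be used in nearly all of them rather than all, and an analysis plan could add a baseline term. This is fair as far as it goes: the protocol does not forbid using Visit 3. But it does commit to particular SELF analyses, none of them baseline-adjusted, directly after announcing a question about change. That is a mismatch in what is written, not a detail left for later.

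A third concerns the two-week list. A reader might call SELF's absence there an error. The documents do not support that: Table 1 classes SELF as a process measure, and the list is of outcomes.

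The gain is also modest. At r of 0.5 or below, adjustment adds almost no power, and the primary HADS anxiety analysis, which already uses baseline, is untouched.

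**Conclusion.** The point holds as a mismatch between the stated question (change) and the named analyses (post-session level), with a baseline scheduled but unused.

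For the arm contrast, the cost is exposure to a chance imbalance with SE 0.71 SD and lost precision if r exceeds about 0.5. For the correlation the weakness is more serious, because randomisation gives no protection. A spurious association of 0.15 to 0.45 can arise with no session effect, given r of 0.5 to 0.9 and a trait–anxiety correlation of 0.3 to 0.5. None of these correlations is in the protocol, so the sizes are illustrative. The mismatch itself does not depend on them.

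Severity is low: this is a secondary process measure in a nine-person pilot that describes its own power as very low.

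**What to change.** In Data Analysis:

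- Keep the SCQ analysis as planned.
- Analyse SELF with Visit 3 as baseline, by ANCOVA or by the condition-by-time repeated-measures ANOVA already used for the other scales. ANCOVA copes better if the arms start unequal. Use the average of the two post-session scores only if the sessions do not differ, as the protocol already requires.
- Correlate post-session SELF with change in HADS and STAI, adjusting for Visit 3 SELF (partial correlation). Do not substitute a simple SELF change score here, for the reason in step 6.
- Optionally, report SELF at Visit 3 versus Visit 10 in the same form.

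The cost is a few sentences and one residual degree of freedom for each adjusted analysis. If r is low (about 0.3), the interval is wider: about 1.08 times post-only for ANCOVA and 1.18 times for the change score. No new assessment is needed, but the Visit 3 and Visit 10 entries in Visit by Visit Description omit SELF and should be aligned with Time and Events so that the baseline is actually collected.
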